5.3. Safety (SAF) Population

The Safety population will contain all patients who are in the Enrolled population and receive at least one dose of study medication (i.e., monotherapy and/or combination therapy).

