6. GENERAL CONSIDERATIONS

6.1. Reference Start Date and Study Day

Study Day will be calculated from the reference start date and will be used to show start/stop day of assessments and events. It will appear in every listing where an assessment date or event date appears.

Reference start date is defined as the day of the first dose of study (combination therapy) (Visit 2), (Day 1 is the day of the first dose of study drug).

- If the date of the event is on or after the reference date, then:
 - Study Day = (date of event – reference date) + 1.
- If the date of the event is prior to the reference date, then:
 - Study Day = (date of event – reference date).

In the situation where the event date is partial or missing, Study Day, and any corresponding durations will appear partial or missing in the listings.

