6.2. Baseline

Unless otherwise specified, baseline is defined as the last non-missing measurement taken same day or prior to reference start date (including unscheduled assessments) before first dose of study medication (i.e., combination therapy). Adverse Events (AEs) and medications commencing on

Document: \\weedc-vnasc01\Biosdata\Menarini\NebAm\ZZA67778\Biostatistics\Documentation\SAP\SAP_Menarini_MEIN21AmNe-Hyp001_Final_V1.0

Author: [name]

Version Number:

Final V1.0

Version Date:

11Nov2022

Template No.: CS_TP_BS016 Revision 7

Reference: CS_WI_BS005

Effective Date: 01Nov2021

the reference start date/time will be considered post-baseline, unless the start time of the AE is known to be prior to the first dosing of the study drug. Since there is no Lab assessment in Visit 2, Lab values collected at Visit 1 will be considered baseline for Lab data.

For combination therapy related analysis, the baseline will be the measurements that are taken at Visit 2 (Week 0). For safety analysis, if the measurement at visit 2 is missing or not collected, then visit 1 data will be considered.

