6.6. Common Calculations

For quantitative measurements, change from baseline will be calculated as:

- Test Value at Visit X – Baseline Value

And for change between Visit 3 and Visit 4 will be calculated as:

- Test Value at Visit 4 – Visit 3 Value

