18.5. Vital Signs

The following Vital Signs measurements will be reported for this study:

- Sitting Systolic Blood Pressure (mmHg)
- Sitting Diastolic Blood Pressure (mmHg)
- Pulse Rate (bpm)
- Respiratory Rate (breaths/min)
- Body Temperature (°C)

The following summaries will be provided for vital signs data:

- Actual and change from baseline by visit for Monotherapy and Combination therapy using the SAF population.
- A by-patient listing of all vital signs data will be presented for both Monotherapy and Combination therapy using the SAF population.

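### The monotherapy vital-sign change in SAP 18.5 has no baseline of its own; the default Visit 2 baseline makes it zero at the end of run-in

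*SAP*

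**What the plan says.** SAP 18.5 lists sitting systolic and diastolic pressure, pulse rate, respiratory rate and body temperature, and plans "Actual and change from baseline by visit for Monotherapy and Combination therapy using the SAF population". It also plans a by-patient listing of all vital signs for both therapies. It does not name a baseline.

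The baseline therefore comes from the general rules:

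- SAP 6.1: "Reference start date is defined as the day of the first dose of study (combination therapy) (Visit 2".
- SAP 6.2: unless another rule is given, "baseline is defined as the last non-missing measurement taken same day or prior to reference start date", and it must be "before first dose of study medication (i.e., combination therapy".
- SAP 6.2, for the combination: "For combination therapy related analysis, the baseline will be the measurements that are taken at Visit 2 (Week 0". No matching sentence covers monotherapy analyses.
- SAP 6.2, fallback: "For safety analysis, if the measurement at visit 2 is missing or not collected, then visit 1 data will be considered".
- SAP 6.6: change is "Test Value at Visit X – Baseline Value".

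The output conventions in SAP Appendix 1 give Visit 2 the label Baseline and Visit 1 the label Screening. The safety population in SAP 5.3 takes in enrolled patients who "receive at least one dose of study medication (i.e., monotherapy and/or combination therapy", so it includes those who only ever took monotherapy.

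**The concern.** Study monotherapy runs from Visit 1 to Visit 2. A baseline taken at Visit 2 sits at the end of that period, so a change measured from it cannot describe what happened during the period.

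Safety and tolerability of the two monotherapies is a secondary objective (Protocol 4). The matching endpoint includes clinically significant abnormal change in vital signs and names Visit 2 among its time points. Protocol 12.5.6 asks for vital signs by visit as change from baseline as well as absolute values. Pulse rate is of obvious interest for a beta-blocker, and the protocol itself excludes patients on heart rate.

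The laboratory, ECG and physical-examination summaries (SAP 18.3, 18.4 and 18.6) are limited to combination therapy. Among these safety summaries, vital signs are the only place where the SAP undertakes to report a change on monotherapy, so the gap matters only there.

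**Working it through.** The documents give no figure to reproduce. The check applies the SAP's own rules to three kinds of patient. The pulse values are assumed, for illustration only.

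**Inputs**

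- Schedule (Protocol 2.2): vital signs at Visits 1, 2, 3 and 4. The first run-in tablets are dispensed at Visit 1 and the first combination tablets at Visit 2.
- Who stops at Visit 2 (Protocol 5, SAP 3.1): patients with controlled pressure, patients who do not tolerate monotherapy, and patients with adherence outside 80% to 120%. They can have a Visit 2 measurement without ever taking the combination.
- Change = value at Visit X minus baseline (SAP 6.6).

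**Patients**

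- A starts the combination: 80, 72, 68, 66 at Visits 1 to 4.
- B is measured at Visit 2 and withdrawn there: 80, 70.
- C leaves before any Visit 2 measurement: 80 at Visit 1.

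**Change at Visit 1 and Visit 2**

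| Patient | Default rule (reference date needed) | Visit 2 baseline with Visit 1 fallback | Visit 1 baseline |
|---|---|---|---|
| A | 80 − 72 = +8; 72 − 72 = 0 | +8; 0 | 80 − 80 = 0; 72 − 80 = −8 |
| B | no baseline | 80 − 70 = +10; 70 − 70 = 0 | 0; 70 − 80 = −10 |
| C | no baseline | 80 − 80 = 0; no Visit 2 value | 0; no Visit 2 value |

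**Reading the table**

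1. Patient A stands for everyone who goes on to the combination with a Visit 2 value. The Visit 2 change is zero whatever the drug did. The true monotherapy change of −8 appears, if at all, as +8 against Visit 1.
2. Patient B took no combination dose, so there is no reference start date and the default rule gives no baseline. The fallback does not help, because it applies only when the Visit 2 value is missing or was not collected. If a programmer uses Visit 2 anyway, the change is zero. Neither result shows the −10.
3. Patient C is covered: the fallback sets the baseline to Visit 1.
4. The Combination columns are unaffected. Patient A has 68 − 72 = −4 at Visit 3 and 66 − 72 = −6 at Visit 4, and these stay as they are if Visit 2 is kept for Combination.

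**How many patients are like B**

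The documents plan 290 screened patients and a cap of 110 per drug at entry to the assessment period. If both caps fill, 290 − 2 × 110 = 70 screened patients (70/290 = 24%) do not start the combination. This is only an upper bound on the monotherapy-only group. It includes screen failures, who are not in the safety population, and patients like C, who have a baseline through the fallback.

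**The case against.** The strongest reply is that this is a gap in wording, not a planned miscalculation. SAP 6.2 allows for exceptions, gives laboratory data a Visit 1 baseline, and ties its Visit 2 sentence to combination analyses. On that view the monotherapy baseline is merely unstated. This does not remove the point. SAP 18.5 states no exception, so the default applies, and the default is Visit 2.

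Several other replies stand and limit the size of the point:

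- A reader might infer that everyone who never starts the combination has no baseline. The safety fallback rules that out for patients with no Visit 2 value.
- A reader might infer that patients who stop during run-in drop out of the vital-sign outputs. They do not. They are in the safety population, and their actual values are tabulated by visit and listed.
- A reader might infer that the blood-pressure effect of monotherapy goes unreported. SAP 16.3.2 analyses systolic and diastolic change from Visit 1 to Visit 2 in the enrolled and mITT populations, and the enrolled population includes patients who never start the combination.
- A reader might take the reversed sign at Visit 1 as certain. It appears only if a change is printed at Visit 1. The by-visit wording allows that, but the table templates are not in the documents.
- A reader might take 70 as the number of patients affected. It is a bound on screened patients, not a count of dosed ones.
- Visit 1 is not an untreated baseline. All patients have been on a beta-blocker or calcium channel blocker for about a month, some on the same drug and dose. For those who continue, the change from Visit 1 to Visit 2 does not show the effect of starting the drug.

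Actual values by visit let a reader subtract one mean from another. They do not give the spread or range of within-patient change, and the patients measured at the two visits may differ.

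**Conclusion.** The point holds in a limited form. Under the SAP's stated rules, the Monotherapy change at Visit 2 is zero for every patient who starts the combination with a Visit 2 value. It is undefined, or zero, for patients with a Visit 2 value who never start. The planned summary therefore cannot show a change on monotherapy at its only scheduled assessment.

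The loss is mainly the within-patient change in pulse rate, respiratory rate and temperature, plus the safety-population version of the blood-pressure change. The number of monotherapy-only patients concerned cannot be derived from the documents. The output is a descriptive safety table, and the primary and secondary efficacy analyses do not depend on it, so this is a minor correction worth making.

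The conclusion assumes that the unseen table templates do not set a separate monotherapy baseline.

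**What to change.** Add one sentence to SAP 6.2, with a cross-reference in 18.5: for Monotherapy vital-sign summaries, baseline is the last non-missing value before the first run-in dose (Visit 1), for all patients in the safety population. State that Combination summaries keep Visit 2.

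The reference date used for study day need not change. Changing it only for patients who never start the combination would give study day two meanings within the same listings.

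The cost is one SAP sentence and minor programming. Visit 1 vital signs are already collected.

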18.6. Physical Examination

The following summaries will be provided for physical examination data for combination therapy by visit on SAF population:

- Shift from baseline according to the physical examination findings.
- Physical Examination parameters will be summarized using the SAF population for the Combination therapy. All Physical Examination data will be listed for both Monotherapy and Combination Therapy using the SAF population.

18.7. Other Safety Assessments

No other safety assessment will be collected for this study.

19. DATA NOT SUMMARIZED OR PRESENTED

The other variables and/or domains not summarized or presented are:

- Comments
- Contacts

Document: \\eedc-vnasc01\Biosdata\Menarini\NebAm\ZZA67778\Biostatistics\Documentation\SAP\SAP_Menarini_MEIN21AmNe-Hyp001_Final_V1.0

Author: [name]

Version Number:

Final V1.0

Version Date:

11Nov2022

Template No.: CS_TP_BS016 Revision 7

Reference: CS_WI_BS005

Effective Date: 01Nov2021

These domains and/or variables will not be summarized or presented, but will be available in the clinical study database, SDTM and/or ADaM datasets.

Document: \\eedc-vnasc01\Biosdata\Menarini\NebAm\ZZA67778\Biostatistics\Documentation\SAP\SAP_Menarini_MEIN21AmNe-Hyp001_Final_V1.0
Author: [name] Version Number: Final V1.0
Version Date: 11Nov2022
Template No.: CS_TP_BS016 Revision 7 Reference: CS_WI_BS005
Effective Date: 01Nov2021

APPENDIX 1. PROGRAMMING CONVENTIONS FOR OUTPUTS

IQVIA Output Conventions

Outputs will be presented according to the following:

[Global Bios > Processes > GBIOS Processes - Implementation Guidelines and Templates > General Guidelines and Templates > Output Conventions.](#)

Dates & Times

Depending on data available, dates and times will take the form yyyy-mm-ddThh:mm:ss.

Spelling Format

English US

Presentation of Treatment Groups

For outputs, treatment groups will be represented as follows and in the given order:

Therapy	Treatment Group	For Tables, Listings and Figures
Monotherapy	NEB 5mg	NEB 5mg
Monotherapy	AML 5mg	AML 5mg
Combination Therapy	NEB+AML (5mg)	NEB+AML (5mg)
Combination Therapy	NEB+AML (10mg)	NEB+AML (10mg)

Presentation of Visits

Visit 1 (Week -4)

Visit 2 (Week 0)

Visit 3 (Week 4)

Document: \\weedc-vnasc01\Biosdata\Menarini\NebAm\ZZA67778\Biostatistics\Documentation\SAP\SAP_Menarini_MEIN21AmNe-Hyp001_Final_V1.0

Author: [name]

Version Number:

Final V1.0

Version Date:

11Nov2022

Template No.: CS_TP_BS016 Revision 7

Reference: CS_WI_BS005

Effective Date: 01Nov2021

Visit 4 (Week 8)
Early Termination

For outputs, visits will be represented as follows and in that order:

Long Name (default)	Short Name
Screening (Visit 1)	Scr (V1)
Baseline (Week 0) or Visit 2 (Week 0)	BL(W0) or V2 (W0)
Visit 3 (Week 4)	V3 (W4)
Visit 4 (Week 8)	V4 (W8)
Early Termination	ET

Listings

All listings will be ordered by the following (unless otherwise indicated in the template):

- Treatment group (Monotherapy and Combination Therapy),
- Center-subject ID,
- Date (where applicable).

Document: \\weedc-vnasc01\Biosdata\Menarini\NebAm\ZZA67778\Biostatistics\Documentation\SAP\SAP_Menarini_MEIN21AmNe-Hyp001_Final_V1.0

Author: [name]

Version Number:

Final V1.0

Version Date:

11Nov2022

Template No.: CS_TP_BS016 Revision 7

Reference: CS_WI_BS005

Effective Date: 01Nov2021

Reference Code

- Paired t-test

```
ods trace on;  
proc ttest data=input_data h0=0;  
  paired VISITX*VISITY;  
  ods output TTests=test;  
run;  
ods trace off;
```

- Normality assumption check

```
ods trace on;  
proc univariate data=indata normal plot;  
  var change from baseline;  
  histogram /normal kernel(color=red);  
  ods output TestsForNormality=norm(where=(test="Shapiro-Wilk"));  
run;  
ods trace off;
```

- Wilcoxon Signed Rank Test

```
ods trace on;  
proc univariate data=indata mu0=0 loccount;  
  var change from baseline;  
  ODS Output TestsForLocation=test LocationCounts=LOCC_one;  
run;
```

- Exact McNemars Test

```
ods trace on;  
ods output McNemarsTest=McNemarsTest;  
proc freq data=indata order=data;  
  tables VISITX*VISITY/agree alpha=0.05 ;  
  exact mcnem;  
  weight ZZZ/zeros;  
run;
```

Document: \\neadc-vnasc01\Biosdata\Menarini\NebAm\ZZA67778\Biostatistics\Documentation\SAP\SAP_Menarini_MEIN21AmNe-Hyp001_Final_V1.0

Author: [name]

Version Number:

Final V1.0

Version Date:

11Nov2022

Template No.: CS_TP_BS016 Revision 7

Reference: CS_WI_BS005

Effective Date: 01Nov2021

- Independent sample t-test

```
ods trace on;  
proc ttest data=indata h0=0;  
class xxx;  
var change from baseline;  
run;  
ods trace off;
```

- Wicoxon Rank Sum Test

```
ods trace on;  
proc npar1way data=indata wilcoxon;  
by by_variables;  
class xxx;  
var change from baseline;  
ods output WilcoxonTest=wt;  
run;
```

- Repeated measures GLM

```
proc mixed data=indata;  
class visit sex;  
model change from baseline = Visit Age Gender BMI baseline_DBP Age*Gender  
Age*BMI_Age*baseline_DBP Gender*BMI Gender*baseline_DBP BMI*baseline_DBP  
Age*Gender*BMI_Age*Gender*baseline_DBP Age*BMI*baseline_DBP Gender*BMI*baseline_DBP  
Age*Gender*BMI*baseline_DBP;  
repeated visit;  
run;
```

Document: \\eedc-vnasc01\Biosdata\Menarini\NebAm\ZZA67778\Biostatistics\Documentation\SAP\SAP_Menarini_MEIN21AmNe-Hyp001_Final_V1.0

Author: [name]

Version Number:

Final V1.0

Version Date:

11Nov2022

Template No.: CS_TP_BS016 Revision 7

Reference: CS_WI_BS005

Effective Date: 01Nov2021

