16.1.4. Supplementary Analysis of Primary Efficacy Variable

A repeated measure general linear model (GLM) will be performed on the primary efficacy endpoint to test the covariate effects and the effects of interactions between the covariates for the mITT population. The GLM model will include change in mean sitting DBP as the dependent variable, repeated through visits Visit 3 (Week 4) and Visit 4 (Week 8). Age (Years), gender, body mass index (BMI), and baseline DBP are considered as the covariates.

The GLM model is

$$\text{Change from Baseline} = \text{Visit} + \text{Age} + \text{Gender} + \text{BMI} + \text{baseline DBP} + \text{Age*Gender} + \text{Age*BMI} + \text{Age*baseline DBP} + \text{Gender*BMI} + \text{Gender*baseline DBP} + \text{BMI*baseline DBP} + \text{Age*Gender*BMI} + \text{Age*Gender*baseline DBP} + \text{Age*BMI*baseline DBP} + \text{Gender*BMI*baseline DBP} + \text{Age*Gender*BMI*baseline DBP}$$

A PROC MIXED procedure, with an unstructured covariance matrix, is used for the analysis and the corresponding p-values for each of the covariates will be presented in a table.

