16.1.5. Sensitivity Analysis of Primary Efficacy Variable(s)

The sensitivity analyses will be conducted similar to the primary efficacy analysis including the repeated measure GLM using the PP population.

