16.2.2. Analysis of Secondary Efficacy Variables

16.2.2.1. Change in mean sitting SBP between Visit 2 (Week 0) and Visit 4 (Week 8)

Change from baseline in sitting SBP from prior and post combination therapy will be compared using paired t-test. The p-value will be presented using a paired t-test comparing mean at baseline and mean at Week 8. The secondary endpoint will be presented in a descriptive manner using n, mean, median, SD, Q1, Q3, and minimum and maximum. Assumption of normality will be investigated using Wilk-Shapiro test. If violation is observed, then paired t-test will be replaced by Wilcoxon signed rank test.

Additionally, the secondary end point of change in SBP between Visit 2 and Visit 4 will be analyzed using a repeated measures GLM as described in Section 16.1.4 with Age (Years), Gender, body mass index, and baseline SBP as covariates to identify the effect of covariates and interaction between the covariates.

16.2.2.2. Change in mean sitting DBP and SBP between Visit 3 (Week 4) and Visit 4 (Week 8)

Change in sitting SBP and DBP between patients under extemporaneous combination of NEB/AML 5/5 mg versus patients uptitrated to the extemporaneous combination of NEB/AML 5/10 mg will be compared using independent samples t-test. The secondary endpoint will be presented in a descriptive manner using n, mean, median, SD, Q1, Q3, and minimum and maximum. Assumption of normality will be investigated using Wilk-Shapiro test. If the data is found to be non-Normal, the independent samples t-test will be replaced by Wilcoxon rank-sum test.

Document: \\needc-vnasc01\Biosdata\Menarini\NebAm\ZZA67778\Biostatistics\Documentation\SAP\SAP_Menarini_MEIN21AmNe-Hyp001_Final_V1.0

Author: [name]

Version Number:

Final V1.0

Version Date:

11Nov2022

Template No.: CS_TP_BS016 Revision 7

Reference: CS_WI_BS005

Effective Date: 01Nov2021

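### The SAP's reference code for the repeated-measures GLM does not specify the model in SAP 16.1.4: it has no patient identifier and no unstructured covariance

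*SAP*

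**What the plan says.** SAP 16.1.4 defines a repeated-measures GLM with change in mean sitting DBP as the outcome, repeated over Visit 3 and Visit 4. The covariates are age, gender, BMI and baseline DBP, with all their interactions. The covariance is explicit: "A PROC MIXED procedure, with an unstructured covariance matrix, is used for the analysis". The purpose is "to test the covariate effects and the effects of interactions between the covariates for the mITT population", and the stated output is that "the corresponding p-values for each of the covariates will be presented in a table".

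The Repeated measures GLM block in SAP Appendix 1 has the class statement "class visit sex" and the repeated statement "repeated visit", closed by a semicolon and followed by `run;`. There is no `RANDOM` statement.

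The model is used in two further places. SAP 16.1.5 repeats the primary analysis "including the repeated measure GLM using the PP population". SAP 16.2.2.1 has the change in SBP "analyzed using a repeated measures GLM as described in Section 16.1.4", with baseline SBP in place of baseline DBP.

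**The concern.** Each patient contributes two changes from baseline, and all the covariates are fixed within a patient. Whether a covariate test is valid depends on the model knowing which two records belong together. The text of 16.1.4 provides for this; the code does not. Protocol 12.5.2 leaves the detail of the GLM to the SAP, so no other document settles which version governs, and SAP 3.3 lists no change to the GLM.

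At stake are the p-values for the covariates and their interactions. If the records are analysed as independent, those p-values are too small on average and covariate effects may be reported that are not there.

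**Working it through.** **Text against code**

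| Element | SAP 16.1.4 | Appendix 1 code |
|---|---|---|
| Covariance | Unstructured | No `TYPE=` option |
| Linking a patient's two records | Implied by the repeated-measures model | No `SUBJECT=`; no patient variable in `CLASS` or elsewhere |
| Gender | Model term Gender | `CLASS` names sex, `MODEL` uses Gender |

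Nothing else in either document supplies the missing options. Without a subject, the whole data set is one block in which each visit level recurs once per patient, so the step may fail to give a valid fit. This was not tested in SAS. The other possibility is that the step is made to run with the records as independent, and the size of that error can be calculated.

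**Inputs**

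- Patients: 216, two records each (Protocol 12.2; SAP 16.1.4).
- Tests: two-sided 5% (SAP 6.5).
- Baseline DBP is the Visit 2 reading (SAP 6.2) and is a covariate (SAP 16.1.4).
- Correlation r between any two of the Visit 2, 3 and 4 readings: not in the documents. Assumed equal for all pairs, with equal variances, and varied from 0 to 0.9.

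The plan states no error rate for this model, so there is no figure of its own to reproduce.

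**Step 1: residual correlation.** With baseline in the model, what matters is the correlation of the Visit 3 and Visit 4 values given the Visit 2 reading. In units of the reading variance, the conditional variance is 1 − r² and the conditional covariance is r − r². Hence

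ρ = (r − r²)/(1 − r²) = r/(1 + r).

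**Step 2: covariate tests.** For a term that is constant within a patient, the independence analysis understates the standard error by the factor 1/√(1 + ρ). The true error of a nominal 5% test is 2 × [1 − Φ(1.96/√(1 + ρ))].

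**Step 3: Visit test.** This is a within-patient contrast, so 1 + ρ is replaced by 1 − ρ.

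Example at r = 0.5: ρ = 0.5/1.5 = 0.333. Covariate terms: 1.96/√1.333 = 1.697, error 9.0%. Visit: 1.96/√0.667 = 2.400, error 1.6%.

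| r | ρ | SE ratio | Covariate test, formula | Covariate test, simulated | Visit test, formula |
|---|---|---|---|---|---|
| 0 | 0 | 1.000 | 5.0% | 5.1% | 5.0% |
| 0.3 | 0.231 | 0.901 | 7.7% | 8.0% | 2.5% |
| 0.5 | 0.333 | 0.866 | 9.0% | 9.3% | 1.6% |
| 0.7 | 0.412 | 0.842 | 9.9% | 9.9% | 1.1% |
| 0.9 | 0.474 | 0.824 | 10.6% | 11.0% | 0.7% |

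The simulated column fits all 15 covariate and interaction terms plus Visit to 216 patients with two records each, and averages the error rate per covariate term. With the two records linked, the same tests ran at about 5% at every r.

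**The case against.** The strongest reply is that Appendix 1 holds templates, not programs. Other blocks use visible placeholders (VISITX, ZZZ, xxx), and this block must in any case be edited before it can serve SBP. A programmer who follows 16.1.4 would fit the right model, and a step that fails to run produces no wrong p-value. This stands to the extent that the consequence is conditional. A reader might infer that the reported covariate p-values will be wrong; the documents show only that the SAP gives two specifications, one of which would produce that result. It does not remove the inconsistency, because this block writes out the trial's own model terms and 16.1.4 and the code cannot both be followed.

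A reader might also argue that the two changes share the Visit 2 reading, so their correlation is about 0.5 and the error about 11% even if the readings are otherwise unrelated. That does not hold. The Visit 2 reading is itself a covariate, which removes the shared part from the residuals; at r = 0 the error is 5%. Under the equal-correlation assumption ρ = r/(1 + r) stays below 0.5, so 11% is about the upper limit. Other correlation structures could give more, but the documents support none in particular.

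It may also be tempting to fault the model for having no Visit-by-covariate terms. That is a modelling preference: 16.1.4 defines the outcome over both visits, and nothing in the SAP contradicts it.

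Finally, the analysis is labelled supplementary and no stated decision rests on it. That is correct and limits the importance of the point.

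**Conclusion.** The contradiction is certain: the printed code does not give the model that SAP 16.1.4 promises. The effect on results is conditional. If the records are analysed as independent, and if visit readings have an equal correlation between 0.3 and 0.9 (residual correlation about 0.23 to 0.47), the standard errors of covariate terms are about 10% to 18% too small. Nominal 5% covariate tests then run at about 8% to 11%, and the Visit test at about 2.5% down to 0.7%. If the code fails to fit, no result is obtained until someone chooses a covariance structure, which the SAP should already have settled.

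The point is confined to the supplementary DBP model, its per-protocol repeat and the SBP model. The paired t-tests for DBP and SBP do not use this code, so the primary conclusion is untouched.

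**What to change.** Replace the two statements in the Appendix 1 block so that they match 16.1.4:

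- `class patient visit gender;`
- `repeated visit / subject=patient type=un;`

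Here `patient` stands for the study's patient identifier. Use one name for gender in both `CLASS` and `MODEL`. The corrected block then serves the mITT and per-protocol DBP models, and the SBP model once baseline SBP is substituted.

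The cost is a few words of code and no new data. Some covariate p-values may be less favourable than the printed code would give if run on independent records.
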